- Cancer-Related Studies (studies with cancer endpoints), Cancer Subjects (e.g., clinical trials, behavior/prevention) or Cancer Specimens (e.g., blood, tissue, cells, body fluids with a scientific hypothesis stated in the protocol). N

Clinical Trials **Yes/No**

- Investigational drugs, biologics, reagents, or chemicals? N
- Commercially available drugs, reagents, or other chemicals administered to subjects (even if they are not being studied)? Y
- Investigational Device / Commercial Device used off-label? N
- IDE Exempt Device (Commercial Device used according to label, Investigational In Vitro Device or Assay, or Consumer Preference/Modifications/Combinations of Approved Devices) Y
- Will this study be registered on# clinicaltrials.gov? (See Stanford decision tree) Y
- Is Stanford responsible for ClinicalTrials.gov registration? (See Stanford decision tree) NCT# Y

Tissues and Specimens **Yes/No**

- Human blood, cells, tissues, or body fluids (tissues)? Y
- Tissues to be stored for future research projects? N
- Tissues to be sent out of this institution as part of a research agreement? For guidelines, please see <https://sites.stanford.edu/ico/mtas> N

Biosafety (APB) **Yes/No**

- Are you submitting a recombinant DNA vector or Human Gene Transfer investigation using biological agents? If yes, please complete and attach the Gene Transfer Protocol Application Supplemental Questions to section 16 of the eProtocol application. N
- Are you submitting a Human study using biohazardous/infectious agents? If yes, refer to the <http://www.stanford.edu/dept/EHS/prod/researchlab/bio/index.html> Administrative Panel on BioSafety website prior to performing studies. N

Title : A double-blind, placebo-controlled, randomized, parallel design study to examine the effectiveness of 10 mg suvorexant in improving daytime sleep in shift workers

Approval Period: Draft

- Are you submitting a Human study using samples from subjects that are known or likely to contain biohazardous/infectious agents? If yes, refer to the <http://web.stanford.edu/dept/EHS/prod/researchlab/bio/index.html> Administrative Panel on BioSafety website prior to performing studies. N

Human Embryos or Stem Cells **Yes/No**

- Human Embryos or Gametes? N
- Human Stem Cells (including hESC, iPSC, cancer stem cells, progenitor cells) N

Veterans Affairs (VA) **Yes/No**

- The research recruits participants at the Veterans Affairs Palo Alto Health Care System(VAPAHCS). N
- The research involves the use of VAPAHCS non-public information to identify or contact human research participants or prospective subjects or to use such data for research purposes. N
- The research is sponsored (i.e., funded) by VAPAHCS. N
- The research is conducted by or under the direction of any employee or agent of VAPAHCS (full-time, part-time, intermittent, consultant, without compensation (WOC), on-station fee-basis, on-station contract, or on-station sharing agreement basis) in connection with her/his VAPAHCS responsibilities. Y
- The research is conducted using any property or facility of VAPAHCS. Y

Equipment **Yes/No**

- Use of Patient related equipment? If Yes, equipment must meet the standards established by Hospital Instrumentation and Electrical Safety Committee [contact]) N
- Medical equipment used for human patients/subjects also used on animals? N
- Radioisotopes/radiation-producing machines, even if standard of care? N
http://www.stanford.edu/dept/EHS/prod/researchlab/radlaser/Human_use_guide.pdf More Info

Payment **Yes/No**

- Subjects will be paid/reimbursed for participation? See payment considerations. Y

Funding **Yes/No**

- Training Grant? N
- Program Project Grant? N
- Federally Sponsored Project? N
- Industry Sponsored Clinical Trial? Y

Funding

Title : A double-blind, placebo-controlled, randomized, parallel design study to examine the effectiveness of 10 mg suvorexant in improving daytime sleep in shift workers

Approval Period: Draft

Funding - Grants/Contracts

Funding Administered By : PAVIR **SPO # (if available) :**

Grant # (if available) : **Funded By (include pending) :** Merck Pharmaceuticals

Principal Investigator : [name]

Grant/Contract Title if different from Protocol Title :

Y For Federal projects, are contents of this protocol consistent with the Federal proposal?
 N Is this a Multiple Project Protocol (MPP)?
 N Is this protocol under a MPP?

Funding - Fellowships

Gift Funding

Dept. Funding

Other Funding

Resources :

a) Qualified staff.

Please state and justify the number and qualifications of your study staff.

[name] is the PI of this study and has conducted studies on human sleep and circadian rhythms for the past 20 years, including clinical trial studies such as this. Drs. [name] and [name] are board-certified sleep physicians and have conducted clinical research projects with [name] in the past. [name] has extensive experience working with clinical trials and been working on such studies with [name] for the past several years.

b) Training.

Describe the training you will provide to ensure that all persons assisting with the research are informed about the protocol and their research-related duties and functions.

[name] will ensure the proper conduct and training of all individuals associated with this project.

c) Facilities.

Please describe and justify.

This is primarily an out-patient study. [name] has assigned office space at VAPAHCS that will be used for recruiting and interviewing participants. The Clinical Studies Unit at VAPAHCS will be used for participant clinical exams.

d) Sufficient time.

Explain whether you will have sufficient time to conduct and complete the research. Include how much time is required.

All staff will have sufficient time to conduct and complete the research. [name], the study

Title : A double-blind, placebo-controlled, randomized, parallel design study to examine the effectiveness of 10 mg suvorexant in improving daytime sleep in shift workers

Approval Period: Draft

coordinator, will spend the majority of her time on this study. [name] will spend approximately 10% of his time supervising this study, [name] will spend approximately 5% of her time advising for this study, and [name] will spend approximately 5% of his time doing participant exams in this study.

e) Access to target population.

Explain and justify whether you will have access to a population that will allow recruitment of the required number of participants.

Healthy volunteers who do shift work will be recruited from the community. Given the prevalence of shift work in the catchment area of this study, we believe that there will be sufficient numbers of participants for recruitment.

f) Access to resources if needed as a consequence of the research.

State whether you have medical or psychological resources available that participants might require as a consequence of the research when applicable. Please describe these resources.

Drs. [name] and [name] will be on 24-hour call in case of medical issues arising during this study.

g) Lead Investigator or Coordinating Institution in Multi-site Study.

Please explain (i) your role in coordinating the studies, (ii) procedures for routine communication with other sites, (iii) documentation of routine communications with other sites, (iv) planned management of communication of adverse outcomes, unexpected problems involving risk to participants or others, protocol modifications or interim findings.

1. Purpose

a) In layperson's language state the purpose of the study in 3-5 sentences.

The purpose of this study is to determine if suvorexant, a drug that inhibits a wake-promoting (hypocretin/orexin) system in the brain, is able to improve day time sleep and night time alertness in individuals who work night shifts.

b) State what the Investigator(s) hope to learn from the study. Include an assessment of the importance of this new knowledge.

There are currently no acceptable therapies to treat day time sleep difficulties in individuals who work night shifts (Shift Work Sleep Disorder). Current pharmacotherapies involve use of benzodiazepines or other sleep medications that put a person into an unnatural state of sleep. The medication being tested in this study blocks a very specific wake-promoting system in the brain that will enable individuals to achieve normal sleep during the daytime.

c) Explain why human subjects must be used for this project. (i.e. purpose of study is to test efficacy of investigational device in individuals with specific condition; purpose of study is to examine specific behavioral traits in humans in classroom or other environment)

The physiology of the drug-targeted system (hypocretin/orexin) being examined in this study is distinct in primates as compared with rodents and other non-mammalian species. The medical condition being examined (Shift Work Sleep Disorder) is uniquely human.

2. Study Procedures

a) Please SUMMARIZE the research procedures, screening through closeout, which the human subject

Title : A double-blind, placebo-controlled, randomized, parallel design study to examine the effectiveness of 10 mg suvorexant in improving daytime sleep in shift workers

Approval Period: Draft

will undergo. Refer to sections in the protocol attached in section 16, BUT do not copy the clinical protocol. Be clear on what is to be done for research and what is part of standard of care.

All procedures are done for research-purposes only.

Baseline visit (3 hours): Consent process followed by baseline assessments using questionnaires, blood draw, urinalysis, electrocardiogram, and physical exam

Week 1-2: Sleep will be monitored with a wrist-worn device that monitors movement as well as participant-completed logs. No changes in behavior.

Weeks 3-5: Sleep will be continued to monitored as during baseline. Subjects will also take a pill 30 minutes prior to day time sleep attempts. This pill will have either drug or placebo (randomized)

End of study visit (2 hour): Same procedures as baseline visit.

- b) Explain how the above research procedures are the least risky that can be performed consistent with sound research design.**

All procedures in this study were designed with the goal of minimizing exposure to risk balanced with gaining a greater understanding of whether this treatment would help the individuals who participate in this study and for whom there is no currently available FDA-approved therapy.

- c) State if deception will be used. If so, provide the rationale and describe debriefing procedures. Since you will not be fully informing the participant in your consent process and form, complete an alteration of consent (in section 13). Submit a debriefing script (in section 16).**

Deception will not be used.

- d) State if audio or video recording will occur. Describe what will become of the recording after use, e.g., shown at scientific meetings, erased. Describe the final disposition of the recordings.**

Audio and video recordings will not occur.

- e) Describe alternative procedures or courses of treatment, if any, that might be advantageous to the participant. Describe potential risks and benefits associated with these. Any standard treatment that is being withheld must be disclosed in the consent process and form. (i.e. standard-of-care drug, different interventional procedure, no procedure or treatment, palliative care, other research studies).**

Instead of participating, individuals who work night shifts can use any one of a number of behaviors or medications to help them sleep during the day time. None of the available pharmacotherapies induce natural sleep and the behavioral therapies have efficacy in only a subset of individuals.

- f) Will it be possible to continue the more (most) appropriate therapy for the participant(s) after the conclusion of the study?**

After conclusion of the study, participants would be able to contact their physicians to obtain a prescription for the medication used in this study.

- g) Study Endpoint. What are the guidelines or end points by which you can evaluate the different treatments (i.e. study drug, device, procedure) during the study? If one proves to be clearly more effective than another (or others) during the course of a study, will the study be terminated before the projected total participant population has been enrolled? When will the study end if no important differences are detected?**

The primary endpoint of this study is a change in total sleep time during day time sleep episodes. Given the blinding of the study and the relatively small population being studied, we do not intend to examine the primary outcome prior to study completion (38 total subjects).

3. Background

- a) Describe past experimental and/or clinical findings leading to the formulation of the study.**

The hypocretins (orexins) are a pair of neuropeptides produced by a small group of hypothalamic neurons

Title : A double-blind, placebo-controlled, randomized, parallel design study to examine the effectiveness of 10 mg suvorexant in improving daytime sleep in shift workers
Approval Period: Draft

that are involved in the regulation of the wake state. As hypocretins are only consistently found in neural tissue and cerebrospinal fluid (CSF), examination of their normal physiologic role in humans has been limited. This is problematic in that the regulation of hypocretins appears to be highly species dependent and related to the manner by which the species consolidates the timing of their sleep and wake. Data from my laboratory, obtained in a series of experiments using the wake-consolidating squirrel monkey (*Saimiri sciureus*), indicate that hypocretin-1 is likely to be the physiologic representation of the mathematically modeled circadian alertness signal. This alerting signal increases in the afternoon and reaches a peak just before habitual bedtime. This signal offsets the increase in homeostatic sleep pressure that accumulates with time spent awake and allows for the consolidation of wake. Importantly, the circadian alertness signal is, as the name indicates, controlled by the central circadian pacemaker located in the hypothalamic suprachiasmatic nucleus. As such, its rise - and the rise of hypocretin-1 in wake-consolidating species such as humans - is determined by internal circadian clock time and is little affected by behavior such as sleep/wake patterns.

While this circadian alerting signal as mediated by hypocretins is indispensable for consolidation of sleep and wake (c.f., sleep and wake fragmentation in those with hypocretin-deficient narcolepsy), it is in direct conflict with obtaining sleep during the daytime, when the circadian alertness signal is working in direct opposition to obtaining sleep. One group of individuals who consistently try to sleep during the biological daytime, when hypocretin-1 concentrations are elevated and opposing sleep, are those who work shifts. According to a survey in 2004 by the U.S. Bureau of Labor Statistics, there are at least 15 million Americans who participate in shift work. While we have the scientific capacity to "flip" the circadian rhythms of individuals working at night and trying to sleep during the daytime, it is a slow process and cannot synchronize individuals who switch between working nights and being awake during the daytime on days off. This leaves two unpalatable options: get poor sleep that is both difficult to initiate and maintain, or take medications such as diphenhydramine (H1 receptor antagonist) or benzodiazepine receptor agonists that induce an artificial and not particularly restful sleep-like state.

Suvorexant provides an ideal solution for improving sleep in shift workers. Histamine H1 receptor antagonists and benzodiazepine receptor agonists force the brain into a state of non-wake. As a dual hypocretin receptor antagonist, suvorexant would suppress the potent circadian drive for wake, thereby creating a permissive state in which natural sleep would be allowed to occur.

b) Describe any animal experimentation and findings leading to the formulation of the study.

see 3a

4. Radioisotopes or Radiation Machines

- a) **List all standard of care procedures using ionizing radiation (radiation dose received by a subject that is considered part of their normal medical care). List all research procedures using ionizing radiation (procedures performed due to participation in this study that is not considered part of their normal medical care). List each potential procedure in the sequence that it would normally occur during the entire study. More Info**

Identify Week/Month of study	Name of Exam	Identify if SOC or Research
------------------------------	--------------	-----------------------------

- b) **For research radioisotope projects, provide the following radiation-related information:**

Identify the radionuclide(s) and chemical form(s).

For the typical subject, provide the total number of times the radioisotope and activity will be administered (mCi) and the route of administration.

If not FDA approved provide dosimetry information and reference the source documents (package insert, MIRD calculation, peer reviewed literature).

Title : A double-blind, placebo-controlled, randomized, parallel design study to examine the effectiveness of 10 mg suvorexant in improving daytime sleep in shift workers

Approval Period: Draft

c) For research radiation machine projects, provide the following diagnostic procedures:

For well-established radiographic procedures describe the exam.

For the typical subject, identify the total number of times each will be performed on a single research subject.

For each radiographic procedure, provide the setup and technique sufficient to permit research subject dose modeling. The chief technologist can usually provide this information.

For radiographic procedures not well-established, provide FDA status of the machine, and information sufficient to permit research subject dose modeling.

d) For research radiation machine projects, provide the following therapeutic procedures:

For a well-established therapeutic procedure, identify the area treated, dose per fraction and number of fractions. State whether the therapeutic procedure is being performed as a normal part of clinical management for the research participants's medical condition or whether it is being performed because the research participant is participating in this project.

For a therapeutic procedure that is not well-established, provide FDA status of the machine, basis for dosimetry, area treated, dose per fraction and number of fractions.

5. Devices

a) Please list in the table below all Investigational Devices (including Commercial Devices used off-label) to be used on participants.

b) Please list in the table below all IDE Exempt Devices (Commercial Device used according to label, Investigational In Vitro Device or Assay, or Consumer Preference/Modifications/Combinations of Approved Devices) to be used on participants.

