examine *retrospective* changes in sleep. These include examining changes in subjective measures of sleep quality that are captured in the BSWSQ, ISI, and FOSQ-10 questionnaires. Changes on these questionnaires will be examined with repeated measure ANOVA. Another exploratory measure to be analyzed in the same manner will be a change in depressive symptom severity as captured on the CES-D. A final exploratory measure will be to examine the change in the number of caffeinated beverages during work shifts. Given that there is tremendous variability in the caffeine content of caffeinated beverages, within subject changes will be examined with multilevel modeling.

Power/Sample Size:

For estimation of sample size, we have reduced our aim to the single, most important outcome measure - will sleep efficiency improve in the drug condition - and reduced the statistical testing to a *t*-test. In previously published work (20), a variance of 3.62% - 3.87% was observed following use of 10 mg of suvorexant or placebo. For purposes of this sample size estimation, we can estimate $\sigma = 5.55\%$ (average variance * 150%, with the increase due to our use of actigraphy instead of polysomnography as a reporter). Setting $\alpha = 0.05$ and power = 80%, we would be able to detect a difference of 5.2% in sleep efficiency (i.e., that which was observed in a previous trial of 10 mg suvorexant in those with insomnia (21)) with 19 participants in each group (n=38 total).

**PROTOCOL
 APPLICATION FORM
 Human Subjects Research
 Stanford University**

Title : A double-blind, placebo-controlled, randomized, parallel design study to examine the effectiveness of 10 mg suvorexant in improving daytime sleep in shift workers

Approval Period: Draft

Protocol Director				
Name [name]		Degree (Program/year if student) PhD		Position, e.g. Assistant Professor, Resident, etc. Asst Professor
Department Psych/Sleep Medicine	Mail Code 5550	Phone [REDACTED]	Fax	E-mail [contact]
CITI Training current				Y

Admin Contact				
Name [name]		Degree (Program/year if student) BS		Position, e.g. Assistant Professor, Resident, etc.
Department Psychiatry and Behavioral Sciences	Mail Code 5550	Phone [REDACTED]	Fax	E-mail [contact]
CITI Training current				Y

Investigator				
Name		Degree (Program/year if student)		Position, e.g. Assistant Professor, Resident, etc.
Department	Mail Code	Phone	Fax	E-mail
CITI Training current				

Other Contact				

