- f) **State the number, if any, of participants who are healthy volunteers. Provide rationale for the inclusion of healthy volunteers in this study. Specify any risks to which participants may possibly be exposed. Specify the measures being taken to minimize the risks and the chance of harm to the volunteers and the additional safeguards that have been included in the protocol to protect their rights and welfare.**

All participants will be healthy volunteers. The main risk to which they are exposed, over the risks they normally encounter in their lives, is taking a prescription medication. There is a favorable side-effect profile with minimal risk reported in taking this medication. The medication being prescribed is being used to specifically treat a sleep disorder in these volunteers.

- g) **How will you identify and recruit potential participants about the research study? (E.g., by: chart**

Title : A double-blind, placebo-controlled, randomized, parallel design study to examine the effectiveness of 10 mg suvorexant in improving daytime sleep in shift workers

Approval Period: Draft

review; notified by treating physician; response to ad). All final or revised recruitment materials, flyers, etc. must be submitted to the IRB for review and approval before use. You may not contact potential participants prior to IRB approval. See Advertisements: Appropriate Language for Recruitment Material.

Participants will be recruited by flyers and online advertising.

h) Inclusion and Exclusion Criteria.

Identify inclusion criteria.

- Aged 20-60 (older individuals excluded due to altered sleep-related circadian signaling)
- Males and females
- Shift worker
 - # Minimum of three months of prior shift work
 - # Will work minimum of four nights per week or 32 hours of night shift per week during study
 - # "Night work" defined as having at least six hours of work occurring between 8 PM and 8 AM and no longer than 12 hours on shift
- Presence of DSM-5 defined Circadian Rhythm Sleep-Wake Disorder: Shift Work Type
 - # Insomnia (SE < 88%) during attempted daytime sleep or excessive sleepiness during nocturnal wake

Identify exclusion criteria.

- Currently or planning to become pregnant
- Currently breastfeeding
- Inadequate opportunity (<7 hours) for daytime sleep after shift work
- Use of sleep aids during the study period. Includes as needed or continuous use of prescription, non-prescription, and naturopathic pharmacotherapies

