The risks of the Radioisotopes/radiation-producing machines (e.g., X-rays, CT scans, fluoroscopy) and associated risks.

None

The risks of the Physical well-being.

The wrist worn activity monitors may cause a rash (contact dermatitis) on the wrist underneath where the device makes contact with the skin. This risk is similar to wearing a wrist watch. If this occurs, we will recommend that participants move the watch and use skin cream on the rash.

The risks of the Psychological well-being.

There is a possibility of increased depressive symptoms following use of this medication. We will monitor this at the end of the first week of drug use. There is always a risk when completing questionnaires that participants will learn something about themselves that negatively affects their psychological well-being.

The risks of the Economic well-being.

Title : A double-blind, placebo-controlled, randomized, parallel design study to examine the effectiveness of 10 mg suvorexant in improving daytime sleep in shift workers

Approval Period: Draft

There is no likely risk to economic well-being.

The risks of the Social well-being.

There is no likely risk to social well-being.

Overall evaluation of Risk.

Low - innocuous procedures such as phlebotomy, urine or stool collection, no therapeutic agent, or safe therapeutic agent such as the use of an FDA approved drug or device.

- b) If you are conducting international research, describe the qualifications/preparations that enable you to both estimate and minimize risks to participants. Provide an explanation as to why the research must be completed at this location and complete the [LINKFORINTERNATIONALRESEARCHFORM] International Research Form. If not applicable, enter N/A.**

n/a

- c) Describe the planned procedures for protecting against and minimizing all potential risks. Include the means for monitoring to detect hazards to the participant (and/or to a potential fetus if applicable). Include steps to minimize risks to the confidentiality of identifiable information.**

Two weeks after initiating the baseline portion of the study, participants will return to the lab and be monitored for risk exposure. One week after initiating medication, subjects will again return to the lab and be monitored for risk exposure.

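### Exploratory questionnaire changes start from a score taken about two weeks before the first pill; repeating the forms at the existing end-of-week-2 visit would be a cheap gain in precision

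*Combined protocol and SAP*

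**What the plan says.** Section 2a (Study Procedures) gives the sequence.

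- **Consent visit:** "Baseline visit (3 hours): Consent process followed by baseline assessments using questionnaires, blood draw, urinalysis, electrocardiogram, and physical exam".
- **Weeks 1-2:** "Week 1-2: Sleep will be monitored with a wrist-worn device that monitors movement as well as participant-completed logs. No changes in behavior".
- **Weeks 3-5:** monitoring continues and "Subjects will also take a pill 30 minutes prior to day time sleep attempts".
- **Close:** "End of study visit (2 hour): Same procedures as baseline visit".

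Section 2a does not name the instruments. Section 2.7 does: the BSWSQ, ISI and FOSQ-10, with the CES-D handled in the same way, all under exploratory measures and described as retrospective. The analysis is one sentence: "Changes on these questionnaires will be examined with repeated measure ANOVA".

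Two further lab visits appear only in Section 9c: "Two weeks after initiating the baseline portion of the study, participants will return to the lab and be monitored for risk exposure", and then "One week after initiating medication, subjects will again return to the lab and be monitored for risk exposure". Their stated purpose is risk monitoring, and no instrument is listed for either. Section 9a names increased depressive symptoms as a possible effect of the drug, to be checked after the first week of dosing.

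By contrast, Section 2.7 has the objective and subjective sleep measures and the alertness ratings collected continuously through both pre-dose weeks.

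**The concern.** A change score is most useful when its first measurement sits just before treatment. Here the last stated pre-dose questionnaire comes about two weeks before the first pill. Anything that moves a participant's answers in those two weeks enters the change score: a bad spell at enrolment that passes, the effect of keeping sleep logs, or ordinary fluctuation.

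Three things are at stake. The between-arm comparison of the exploratory scales may be noisier than it need be in a trial of 38. A within-arm change, if reported, mixes pre-dose drift with what happened on treatment. And for the CES-D, which bears on a risk the protocol itself names, no score is stated near the start of dosing.

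**Working it through.** **The plan's own figure.** The only sample-size figure concerns sleep efficiency, not the questionnaires. With a difference of 5.2, SD 5.55, 80% power and alpha 0.05 (taken as two-sided, since the plan does not say), a two-sample t-test needs 18.89, so 19 per arm, with power 80.2%. The 19 per group reproduces. It sets the number available for the questionnaires but was not chosen for them.

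**Timing.** Consent score to final score is about 2 + 3 = 5 weeks. The pre-dose share is 2/5 = 40%. From the week-2 visit to the final score is about 3 weeks.

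**Precision, raw change.** With two time points, the group-by-time test in a repeated-measures ANOVA is a t-test on change scores, whose variance is 2·SD²·(1 − r), where r is the correlation between first and last score. The documents give no r, so these values are assumptions. With baseline adjustment instead, the residual variance is SD²·(1 − r²).

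| r at 5 weeks → r at 3 weeks | Raw change: (1 − r₃)/(1 − r₅) | Adjusted: (1 − r₃²)/(1 − r₅²) |
|---|---|---|
| equal | 1.00, no gain | 1.00, no gain |
| 0.50 → 0.55 | 0.45/0.50 = 0.90, 10% lower | 0.6975/0.75 = 0.93, 7% lower |
| 0.50 → 0.60 | 0.40/0.50 = 0.80, 20% lower | 0.64/0.75 = 0.85, 15% lower |
| 0.60 → 0.70 | 0.30/0.40 = 0.75, 25% lower | 0.51/0.64 = 0.80, 20% lower |

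**A more favourable assumption.** If correlation decays geometrically with a weekly value of 0.80 to 0.95, the raw change variance falls to 0.73 to 0.63 of its present value, and the adjusted variance to 0.83 to 0.66. The difference detectable at 19 per arm with raw change scores (80% power, normal approximation, 2.80·√[4(1 − r)/19] in SD units) goes from 1.05 to 0.90 SD at 0.80, or from 0.61 to 0.49 SD at 0.95. This model has no stable personal level and no fixed measurement error, so it flatters the shorter gap.

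**Using both pre-dose scores.** If all pairs of scores correlate equally at r, substituting one baseline for the other gains nothing, but adjusting for their mean does: the squared correlation with the final score becomes 2r²/(1 + r). At r = 0.5 this is 0.333, so the adjusted variance is 0.667/0.75 = 0.89 of that with one score. At r = 0.6 it is 0.45, giving 0.55/0.64 = 0.86.

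**Bias.** In 20,000 simulated trials (19 per arm, weekly correlation 0.9, no drug effect), a pre-dose shift common to both arms was added.

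| Shift (SD) | Mean within-arm change (SD) | Within-arm test significant | Between-arm type I error |
|---|---|---|---|
| 0 | 0.00 | 5% | 0.050 |
| 0.3 | 0.30 | 28% | 0.051 |
| 0.5 | 0.50 | 63% | 0.048 |

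The mean between-arm difference stayed within about 0.002 SD of zero. The shift sizes are assumptions.

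**The case against.** The strongest reply is that nothing confirmatory is affected. All four scales are exploratory, randomisation makes pre-dose drift cancel between arms, and a placebo-controlled trial should not be read within arm. That stands. What remains is precision, plus the fact that Section 2.7 does not name the group-by-time term, so a within-arm or overall time effect is not ruled out as the reported result. That omission is a separate gap, and moving the baseline would not by itself close it.

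Several stronger readings are tempting and go beyond the documents.

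- **That no questionnaire will be taken at week 2.** Section 2a answers a prompt for a summary and omits the Section 9c visits altogether. Its silence shows only that none is stated.
- **That run-in mood changes cannot be told from drug effects.** Section 9a plans a mood check after one week of dosing, and Section 9c describes the week-2 visit in similar terms. A pre-dose mood check is possible, though no instrument is named.
- **That participants stop sleep aids at entry and so shift during weeks 1-2.** Section 8h excludes "Use of sleep aids during the study period. Includes as needed or continuous use of prescription, non-prescription, and naturopathic pharmacotherapies" and states no earlier lookback, whereas digoxin and the CYP3A drugs carry six months. Stopping at entry is therefore conceivable. But the criterion describes whom to exclude, not a withdrawal period, Section 2a expects no behaviour change, and nothing indicates how many would stop or by how much scores would move.

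The documents also give no recall windows. If an instrument looks back more than two weeks, a week-2 score would still cover some time before the study, and the benefit would be smaller.

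**Conclusion.** The point holds as an optional, inexpensive improvement. As stated, each exploratory questionnaire change covers about five weeks, of which 40% is before any pill, while an existing visit at the start of dosing has no questionnaire listed. The between-arm comparison remains valid, and the primary and secondary sleep and alertness outcomes are unaffected.

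The size rests on correlations the documents do not give. Substituting the week-2 score gains nothing if the 3-week and 5-week correlations are equal. With a rise of 0.05 to 0.10 from 0.5 or 0.6, variance falls about 10-25% for raw change or about 7-20% with baseline adjustment. Only steady geometric decay gives more. The case for a CES-D score close to the first pill does not depend on these figures, since it follows from the risk named in Section 9a.

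**What to change.** In Section 2a, add the ISI (day and night forms, both listed in Section 16), BSWSQ, FOSQ-10 and CES-D to the existing end-of-week-2 visit, completed before the first pill. If this is already intended, say so.

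In Section 2.7, replace the repeated-measures sentence with a comparison of arms on the end-of-study score, adjusted for the pre-dose score. Fix in advance whether that is the week-2 score or the mean of the consent and week-2 scores. The mean does better if correlations hardly change with the gap, and the week-2 score does better if they fall off steadily. State each instrument's recall window so that the choice can be judged.

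The cost is a few minutes of participant time at a visit that already takes place, and a line in each section. No visit is added and the sample size stays at 38.
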